6.0 Enrollment/Randomization

We aim to study N = 4 subjects, although seek approval enrolling up to 6 subjects due to the small sample size of 4 and the need for high adherence. Based on study diet and urine and fecal collection adherence of >90%, N = 2 patients that meet this level of adherence will be asked to continue with the full balance and kinetics protocol (Aim 2) on a first-enrolled basis. Thus 2 subjects will complete the absorption study (Aim 1), and 2 subjects will complete the full balance and kinetic studies (Aim 1 and Aim 2). It will be determined before a subject signs consent which consent they will sign (Consent A = Aim 1 or consent B= Aim 1 and Aim 2).

Recruitment will target moderate stage CKD patients aged 30-75 years old. Subjects will be recruited from patients seen in CKD clinics of the IU/Eskanazi Nephrology group who are partners of the co-investigators.

- Personnel from the IUSM Division of Nephrology will review medical charts from nephrology clinics for pre-screening to determine potential eligibility. An email will be sent to the doctors of the identified potential subjects to obtain their permission for enrollment and the potential subjects will be contacted by phone or visited by study staff during clinic.
- Information about the study may be discussed with interested potential subjects by research personnel by phone, email or in person as preferred by the subject/clinic.
- If interested, potential subjects will be either 1) scheduled for a screening visit at the Indiana Clinical Research Center, or 2) have screening information collected at the time of recruitment if subject is recruited in person at a CKD clinic by study staff.
- Prior to screening, subjects will be asked to provide written informed consent, and will be given the opportunity to have their questions about participation answered.
- Following the screening visit, all data will be evaluated by the study staff to determine eligibility of the subject. If eligible, participants will be enrolled in the study, and study visit dates will be scheduled.

Randomization Plan

At the beginning of the study, the study biostatistician will generate a randomization list for dietary intervention crossover order A or B by pairs. These orders will be A=LCa/HP to LCa/LP and B=LCa/LP to LCa/HP. Especially due to the small sample size, attention will be made to ensuring a balance of the two orders, which will be accomplished by randomizing both in pairs.

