11.0 Study Withdrawal/Discontinuation***Diet Adherence Assessment***

Patients will be assessed for adherence to the controlled diet on Day 3 of the controlled diet outpatient period. Subject who do not meet a minimum 90% adherence will be withdrawn from the study. This will be determined by evaluating meal check lists and returned uneaten foods. During the 48-hour absorption testing as inpatients, subjects must show at least 90% adherence with the study diet and complete urine and fecal collections to be eligible to continue the additional 12-days (5 as inpatient) for full balance and kinetic measures. This is to ensure high quality balance data for these preliminary studies.

Participants may withdraw themselves from the study at any time by informing the study staff. The study staff may ask the participant if they are willing to talk about their reason for wanting to withdrawal from the study and if they are willing to discuss potential accommodations that might be possible that would make continuing the study possible, if appropriate. The study staff will explicitly let the participants know that they are not obligated to give a reason or discuss ways they might change their mind.

For participants who do not complete the entire study, data for the completed portions will be used for secondary/exploratory analyses, when statistically appropriate, unless the subject withdraws their consent for use of their data.

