12.0 Statistical Considerations

This is a pilot study to determine effect sizes and variance estimates in fractional Ca, P, and Mg intestinal absorption (Aim 1) and Ca, P, and Mg balance (Aim 2) in patients with moderate CKD on a low Ca/High P (LCa/HP) diet vs. low Ca/low P (LCa/LP) diet. These data will be used for power calculations to determine an adequate sample size for a subsequent clinical trial to be proposed in an R01.

Four participants will be enrolled in this randomized cross-over study, 50% female, and we aim for at least ¼ black/African American and at least ¼ white race. All N = 4 will be included in Aim 1 with the primary outcomes of fractional Ca, P, and Mg absorption from a 48-hour testing periods. A subset of N = 2 subjects will be studied under Aim 2, with a week of Ca, P, and Mg balance and full kinetic model (12 days (5 as inpatient) beyond the initial 48-hour inpatient absorption test protocol).

At the beginning of the study, the study biostatistician ([name]) will generate a randomization list for dietary intervention crossover order A or B by pairs. These orders will be [LCa/HP to LCa/LP] or [LCa/LP to LCa/HP]. Especially due to the small sample size, attention will be made to ensuring a balance of the two orders, which will be accomplished by randomizing both in pairs.

Based on our experience, we anticipate only a 15% attrition rate, which is only 0-1 enrolled subjects needing to be replaced. However, because of the small sample size of 4 and the need for high adherence due to the preliminary nature of these studies, we seek approval enrolling up to 6 subjects to complete our planned n = 4.

Statistical Analysis: A repeated measures analysis of variance (ANOVA) for cross-over designs will be used to compare the LCa/HP diet with the LCa/LP diet on the primary outcomes:

Aim 1:	Aim 2:
Fractional Ca Absorption	Ca Balance
Fractional P Absorption	P Balance

Data will be examined for outliers and distributional model assumptions will be checked. Remedial measures will be taken as needed.

Power Calculations: The sample size required for the future R01 proposal will be based on the mean differences observed in the primary outcomes between the LCa/HP and LCa/LP diets, as well as the within- and among-patient variance estimates. We will determine sample sizes needed to detect a range of mean differences between diets with 80% to 90% power for a cross-over study.

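### Opposite diet orders in the two Aim 2 subjects are not protected if one fails an adherence check or is replaced, and two subjects cannot supply a usable variance for Aim 2

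*Combined protocol and SAP*

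**What the plan says.** **Order.** The Randomization Plan in 6.0, repeated in 12.0, describes a single list made at the start of the study: the biostatistician "will generate a randomization list for dietary intervention crossover order A or B by pairs". Order A is high P then low P; order B is the reverse. Because the sample is small, "attention will be made to ensuring a balance of the two orders". Neither section splits the list by Aim or by consent group.

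**Entry to Aim 2.** Section 6.0 gives two accounts. Subjects who meet the adherence level "will be asked to continue with the full balance and kinetics protocol (Aim 2) on a first-enrolled basis". The same paragraph also says: "It will be determined before a subject signs consent which consent they will sign", with Consent A covering Aim 1 only and Consent B covering both Aims.

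**Adherence checks.** Section 11.0 sets two. At Day 3 of the outpatient diet: "Subject who do not meet a minimum 90% adherence will be withdrawn from the study". During the 48-hour inpatient test, "subjects must show at least 90% adherence with the study diet and complete urine and fecal collections to be eligible to continue" into the Aim 2 phase.

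**Replacement.** Section 12.0 says: "we anticipate only a 15% attrition rate, which is only 0-1 enrolled subjects needing to be replaced". Up to six may be enrolled to complete four. The order that a replacement receives is not stated.

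**Use of the data.** Section 12.0 applies a cross-over ANOVA to calcium and phosphorus absorption (Aim 1, four subjects) and balance (Aim 2, two subjects). The mean differences and the within- and among-patient variances feed the sample size of a later trial. Aim 2 in 2.0 also promises effect sizes and variance estimates.

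**The concern.** A two-period cross-over separates diet from period only if both orders occur. With four subjects in two pairs this is secure. In Aim 2 it rests on two people having opposite orders, and the plan secures that only on the path where nothing goes wrong.

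The controlled diet starts on Day 1, so both checks in 11.0 come after the subject has begun an assigned order. A subject who fails has already used a list slot. What follows is not written down: a replacement could take the vacated order or the next one on the list. Fixing the consent group before signing also means that Consent B need not follow list position.

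Four of the six primary outcomes in 3.1 (calcium and phosphorus balance, calcium and phosphorus kinetics) come from the Aim 2 subset. If its two members share an order, none of the four has a diet estimate separate from a change between periods, and no analysis can restore it. A second issue remains whatever the orders: two subjects cannot yield the variance that 2.0 and 12.0 say Aim 2 will provide.

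**Working it through.** **1. The plan's own figure.** Inputs from 12.0: four subjects, 15% attrition. Expected losses are 4 × 0.15 = 0.6. Inflating, 4 / 0.85 = 4.7, rounded up to 5, which is one replacement. This agrees with the stated 0-1.

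**2. Estimability in Aim 2.** Let δ be the diet effect (high P minus low P), π the period effect (period 1 minus period 2), and d each subject's period 1 minus period 2 difference. Then E(d) = π + δ for order A and π − δ for order B.

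- Opposite orders: (d_A − d_B)/2 estimates δ. The model with subject, period and diet has 4 columns and rank 4 on 4 observations, so residual df = 0.
- Same order: both differences estimate π + δ (or π − δ). Rank is 3 of 4, and diet is not estimable apart from period. There is 1 residual df, and it is free of any period effect.
- Opposite orders with period left out: rank 3, 1 residual df, valid only if π = 0.
- Aim 1 with four subjects, split 2:2 or 3:1: full rank, 2 residual df. The problem is confined to Aim 2.

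**3. Chance of a shared order.** Let f be the probability that a subject fails. It is an assumption: the 15% in 12.0 is overall attrition, not a failure rate for the checks in 11.0. Two subjects from one pair never share an order; two from different pairs share one with probability 1/2.

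- No failure among the first two, or a replacement takes the vacated order: 0.
- First two who qualify, next list slot used, long list: the first qualifier is the first member of a pair with probability 1/(1 + f), and the partner then qualifies with probability 1 − f. So P(shared) = ½[1 − (1 − f)/(1 + f)] = f/(1 + f).
- Consent B fixed for the first two enrolled, replacements from slots 5 then 6, given that four succeed: P(shared) = (f + 3f²)/(1 + 4f + 10f²). At f = 0.15 this is 0.2175/1.825 = 0.119; at f = 0.05 it is 0.0575/1.225 = 0.047.

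| Rule for filling places | f = 5% | f = 15% |
|---|---|---|
| Replacement takes vacated order | 0 | 0 |
| Consent B fixed, next slot, four succeed | 0.047 | 0.119 |
| Consent B fixed, next slot, two Consent B succeed | 0.047 | 0.126 |
| First two qualifiers, six slots | 0.048 | 0.130 |

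**4. What 1 df is worth.** The 95% interval for an SD is the estimate times √(1/χ²) at the 0.975 and 0.025 quantiles. With 1 df these are √(1/5.024) = 0.45 and √(1/0.000982) = 31.9.

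**The case against.** The strongest reply is that the plan is already balanced where it matters. First-enrolled entry together with paired orders makes the first two subjects a pair, and only a failure or replacement breaks this. The stated wish to balance the orders would naturally lead staff to give a replacement the vacated order, and the chance of a shared order would then be 0. Two sentences in 6.0 can also be read together: offer Consent B to the first two enrolled, and let continuation depend on the 48-hour check. All of this stands, and it limits the point to what happens after a failure. It does not close the gap, because neither the replacement rule nor the link between Consent B and list position is written. The Randomization Plan's closing remark that both are randomised in pairs most naturally means both orders. Even if it meant both Aim groups, it would not cover a replacement.

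A reader might infer that nothing connects the Aim 2 subjects to a pair, or that the risk is 1/3 (Consent B falling at random among two A-order and two B-order subjects) or 1/2 (the two coming from different pairs). The documents do not support these as general figures. The first sets aside the first-enrolled wording, and the second is conditional on the pair having already been broken.

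Two further replies have force. The same-order case leaves 1 period-free residual df, whereas opposite orders with period fitted leave none, so protecting the point estimate gives up that df. Given the interval in step 4, the practical loss is small. And this is a pilot with controlled feeding, a 7-day equilibration and a 1-3 week washout; 12.0 does not say whether period will be fitted, and nothing in the documents shows a period effect to be likely.

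**Conclusion.** The point holds in a limited form. Aim 2 is balanced if the first two enrolled both continue. It is unprotected if one of them fails a check in 11.0 or is replaced, and it need not be balanced if Consent B is given without regard to list position. A shared order removes any diet estimate separate from period for calcium and phosphorus balance and kinetics.

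The size is 0 under replacement into the vacated order, and about 5% to 13% under next-slot replacement at assumed failure rates of 5% to 15%. These figures use one failure rate for everyone, although the 48-hour check applies only to continuing into Aim 2. A reader should not infer that Aim 2 is likely to be confounded or that its result would be biased: what is at stake is whether a two-person point estimate can be interpreted.

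The variance statement does not depend on any failure rate. With opposite orders Aim 2 has 0 residual df once period is fitted, and 1 df, with an SD known only to within 0.45 to 31.9 times its estimate, if period is dropped. It cannot supply a usable within-patient variance for the later sample size.

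**What to change.** 1. In 6.0 and 12.0, randomise one AB/BA pair within each consent group, and give each replacement the order and consent group of the subject replaced. The minimum version is one sentence: keep first-enrolled entry and have a replacement take the vacated order.
2. In 6.0, reconcile first-enrolled entry after adherence is seen with a consent group fixed before signing.
3. In 2.0 (Aim 2) and 12.0, state that two subjects with opposite orders give a diet point estimate only, with the residual df set out above, and that the within-patient variance for balance in the later sample size must come from elsewhere or be treated as unknown.

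**Cost.** A new list and a few sentences. A replacement's order is known before enrolment; for the planned four, predictability is unchanged, since the second member of any pair is already known. A Consent B subject who fails must be replaced by another Consent B subject, where otherwise someone already enrolled might have stepped in. At least one such replacement is needed with probability 1 − (1 − f)²: 10% at f = 5% and 28% at f = 15%. Both groups share the two spare places. If every failure is replaced, fewer than four succeed within six in 0.2% and 4.7% of trials at those rates, on the same single-rate assumption.

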7.0 Study Procedures

All study procedures will be conducted for the purpose of research.

Screening Visit

Following informed consent, a screening visit of approximately 60 minutes to assess eligibility will include a medical history, renal panel, and urine albumin/creatinine ratio (UACR). Recent lab values from the medical chart within ~3 months may be used if available. eGFR will be calculated from serum creatinine using the CKD-EPI equation (20). A urine pregnancy test of human gonadotropin will be performed for subjects of childbearing potential.

Pre-Study Washout Period and Run-In Period

Otherwise eligible subjects who take drugs that potentially alter calcium and phosphate balance or homeostasis including high dose cholecalciferol or ergocalciferol (1000 U/day or 50,000 U/wk, respectively), active vitamin D metabolites, calcimimetics, PTH analogues in the last 30 days, will undergo a 30-day pre-study washout from these drugs to be eligible for the study, with their physician approval.

All subjects will be given 600 IU/d of an oral vitamin D supplement (cholecalciferol) for 2-weeks prior to beginning the controlled feeding period and through completion of the study. This is to ensure vitamin D intake adequacy prior to the study, as was done for our previous balance study in CKD patients(14). 600 IU/d is the current recommended dietary allowance from the Institute of Medicine (18).

Dietary Interventions

The cross-over will consist of a randomly assigned order of two dietary conditions:

1) Low Ca (500 mg/d)/high P (1500 mg/d) diet (LCa/HP)

The LCa/HP diet is at levels within the range observed for a typical American diet poor in Ca and high in P (18-21)

2) Low Ca (500 mg/d)/low P (800 mg/d) diet (LCa/LP)

The LCa/LP diet represents coupling a typical poor Ca intake with the commonly prescribed dietary P restriction of 800 mg/d (22).

The magnesium content will be identical in both diets. Diets will be designed by a registered dietitian of the Bionutrition Center of the Indiana CTSI using nutrient analysis software, and mineral composition will be confirmed by chemical analysis of diet composites prior to and during the studies. The LCa/LP diet will be designed to contain zero-to-minimal phosphate food additives, and an equal portion of protein from animal and plant sources. The LCa/HP diet will be achieved in part through higher amounts of phosphate food additives, which is representative of a typical American diet. Diet levels will be designed to be as close to the above targets,

but final values may differ by approximately +/- 10%. Actual levels of the diets will be reported in the results of this study

All meals will be prepared in the metabolic kitchen at the Indiana CTSI CRC, with ingredients weighed with precision to 0.1 g. Outpatient meals will be provided as pack-outs for the subjects to take home; Inpatient meals will be prepared and trayed for the subjects. Diet composites will be prepared alongside subject diets, homogenized, ashed, and analyzed for accurate dietary Ca, P, and Mg intakes during the balance studies. Any leftovers not eaten will be weighed back and chemically analyzed and considered in the balance calculations (Aim 2).

A non-absorbable fecal marker, polyethelene glycol (PEG), molecular weight 3350, will be given in capsule form ~1 g with each meal (~3 g/d), to assess % fecal PEG recovery for fecal collection compliance, as well as steady-state by fecal Ca:PEG, P:PEG, and Mg:PEG ratios (23). This will be in the meal pack-outs or on the patient meal trays while inpatient.

Baseline Measures

A baseline outpatient visit of approximately 60 minutes will occur on "Day 1" of the study. This is when the controlled research diet will begin. Subjects will arrive to this appointment fasting at least 8 hours and will have blood and urine collected for baseline biochemistries. These will include a renal panel, serum 25D, and urine Ca, P, creatinine, and additional serum collected for additional measures such as baseline bone and mineral biochemistries and uremic retention solutes. eGFR will be calculated from serum creatinine using the CKD-EPI equation (17). Subjects will receive 3 days of meal pack-outs and will return on the 3rd or 4th day for the remaining meals until the inpatient stay. We will obtain meal adherence data over the outpatient period using meal checklists, PEG capsule pill counts, and leftover food weigh-backs. Anthropometrics (weight, and height) and vital signs will be taken at the baseline visit. Subjects will also be asked to bring a stool collection from home to the Day 1 visit, the stool sample should be collected within 3 days prior to the visit. Stool collection supplies will be given to the subjects at the screening visit.

Ca, P, Mg Absorption Tests (Aim 1)

Following the 7-day outpatient equilibration period on the controlled diet, participants will be asked to fast overnight at least 8 hours and will be admitted to the Indiana CTSI clinical research center (CRC) on the morning of study Day 8. Subjects will continue the controlled diet for the 2-day inpatient testing. We will collect fasting blood and urine, and then subjects will be given their assigned diet breakfast with a beverage containing 10 μ Ci P-33 (range 8-11 uCi) and 10 mg stable Ca-44(range ~8-11 mg), and 40-70 mg Mg-26 to drink halfway through their meal. Blood samples will be taken pre-dose, then 5, 15, 30, 60, 90, 120, 180, 240, 360 min, and 24h post-dose. All urine will be collected during the test days in 2-hour intervals until 6-hours post-dose, and then 6h-24h post-dose with collections timed and recorded by CRC staff. These urine collections will be individually measured for volume and a small aliquot taken for time point measurements, and then we will combined the values of the intervals to give a total 24h value. On Day 9, subjects will receive the same breakfast as Day 8, at the same clock time, but with no isotope; at 25h post-oral dose, an IV push of 10 μ Ci P-33 (range 8-11 uCi) and 6 mg stable Ca-44 (range ~5-7 mg), and 20-30 mg stable Mg-25 in sterile saline will be given over 2 minutes. Serum and urine collections post-dose will follow the same time points as during Day 8 and will continue through the 24-hour post-IV dose on Day 10, prior to discharge. The amount of isotope in the sequential blood and urine samples will be determined by liquid scintillation counting or inductively coupled plasma mass spectrometry for P-33 and Ca-44/Mg-25/Mg-26, respectively. Time points are approximate, and exact clock time of blood and urine collections will be recorded throughout the inpatient study and used in the kinetic analysis. Thus, only missed time point collections will be considered protocol deviations.

Ca, P, Mg Balance and Kinetics (Aim 2)

For the full Ca, P, Mg balance and kinetics in Aim 2, a subset of N = 2 subjects will remain inpatient for an additional 5 days following the 48-hour absorption testing protocol described under Aim 1. During this time, all urine and fecal samples will be collected. Urine will be collected in time, 24-hour pools, as well as two 2-hour fasting urine collections taken on the morning of Day 15, aliquoted for fasting biochemistries, and then data combined with the appropriate 24-hour collection. Urine Ca, P, Mg and creatinine will be measured in each 24-hour collection or 2-hour fasting collection. Blood samples will be taken each morning, Day 10-15, to use for full Ca, P, and Mg kinetic modeling. Subjects will be discharged the morning of Day 15, after the 2-hour fasting urine and fasting blood collection; at this point they will discontinue study diet and PEG, but continue taking vitamin D at home for the remainder of Day 15 through Day 21. Fasting blood biochemistries will be measured in samples collected during a return outpatient visit on Day 21. In addition to isotope analysis, total serum Ca, P, Mg and creatinine will be measured by standard clinical chemistries. All fecal samples will be collected during the inpatient periods, then homogenized, ashed, and analyzed for Ca-44, P-33, Mg-25, Mg-26, total Ca, total P, total Mg, and PEG recovery.

Other Biochemistries

Additional biochemistries will be measured in serum and urine samples collected during these studies. These will include FGF23, PTH, 1,25D at the end of the study and creatinine clearances. The sequential and timed serum and urine samples will allow for dynamic assessment of these biochemical outcomes. Data on additional minerals Na, K, and Mg will be obtained from the ICP analysis of urine, diet, and feces, and may be used in secondary analyses. Additional analyses on leftover serum, urine, or feces may include other mineral metabolism biochemistries (e.g. 25-hydroxyvitamin D or bone turnover biomarkers), metabolites considered to be gut-derived uremic retention solutes (e.g. TMAO). The fecal microbiome may be analyzed in secondary analyses.

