4.0 Eligibility Criteria

4.1 Inclusion Criteria

- Men or women, ages 30-75 years old, any race or ethnicity
- Moderate CKD, defined by KDIGO as eGFR category 3b (30-44 mL/min), with albuminuria categories A1-A3 (**Figure 1**)
- Female subjects must be postmenopausal (>12 months since last menstrual period), surgically sterile, or confirmed not pregnant by pregnancy test
- Must be on stable doses of medications (except those noted in exclusion criteria) for at least 4 weeks prior to the study
- Willing to discontinue nutritional supplements (e.g. vitamin D, calcium, multivitamin/minerals, or others) upon enrollment until completion of the study
- Adequate vitamin D status defined as serum 25D > 20 ng/mL

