4.2 Exclusion Criteria

- Plans to initiate dialysis within 6 months
- Hypercalcemia defined as serum calcium >10.5 mg/dL within past 3 months
- Hyperkalemia defined as serum potassium >5.5 mg/dL within past 3 months
- Hyperphosphatemia defined as serum phosphate >5.5 mg/dL within past 3 months
- Intestinal disease that alters absorption or normal intestinal function including celiac disease, small bowel resection, or bariatric surgery
- Serious, *uncontrolled* underlying systemic disease including diabetes, lupus, hypertension (as deemed by the PI).
- Pregnant or breastfeeding
- Taking a phosphate binder medication, calcitriol, vitamin D analogs, calcimimetics, PTH analogues, and other medications that may alter Ca and P metabolism within past 30 days
- Vegan or vegetarian diet, lactose intolerance and/or milk allergy

Figure 1. Current CKD Nomenclature Used by KDIGO Guidelines

[figure not shown]
Green: low risk (if no other markers of kidney disease, no CKD); Yellow: moderately increased risk; Orange: high risk; Red, very high risk.

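### The supplied text places the only pregnancy test at screening, at least 21 days before the first P-33 dose, and does not tie the pregnancy criterion to the dosing days

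*Combined protocol and SAP*

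**What the plan says.** Section 4.1 accepts female subjects who are postmenopausal, "surgically sterile, or confirmed not pregnant by pregnancy test". The age range starts at 30, so some women of childbearing potential may enrol. Section 4.2 lists "Pregnant or breastfeeding" as an exclusion. Neither section gives a time point for confirming this.

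The test itself appears once, in Section 7.0 under Screening Visit: "A urine pregnancy test of human gonadotropin will be performed for subjects of childbearing potential".

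The intervals that follow screening are also in Section 7.0. Every subject takes vitamin D "for 2-weeks prior to beginning the controlled feeding period". Subjects on certain drugs "will undergo a 30-day pre-study washout from these drugs to be eligible for the study". The first absorption test comes "Following the 7-day outpatient equilibration period on the controlled diet", on Day 8. That morning, "We will collect fasting blood and urine, and then subjects will be given their assigned diet breakfast with a beverage containing" P-33 and the stable tracers. The IV P-33 dose is given on Day 9, 25 hours after the oral dose. Section 5.0 repeats the sequence on the other diet after a washout of 1 to 3 weeks. Section 10.0 counts four P-33 doses in all.

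No repeat pregnancy test is mentioned in the crossover description (Section 5.0), the Day 1, Day 8 or Aim 2 procedures (Section 7.0), the radiation risks and protections (Section 10.0) or the withdrawal rules (Section 11.0). Section 8.0 refers to Appendix B for the study calendar; its content is not in the supplied text.

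**The concern.** The exclusion matters most when the radiotracer is given. A screening test can detect a pregnancy already established that day. It cannot detect one that begins afterwards, and the schedule always puts weeks between the test and the first dose. Section 4.1 states no contraception requirement that would cover the interval.

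A woman who conceived after screening could therefore receive up to four P-33 doses without any procedure in the supplied text showing that she no longer meets the criterion. What is at stake is a participant-safety criterion. No sample-size, power or error-rate figure is involved.

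**Working it through.** The plan gives no figure for the interval from test to dose, so it is built from the stated durations. Screening is day 0, and the run-in (or drug washout) is taken to start that day.

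**Inputs**
- Vitamin D run-in: 14 days, all subjects (Section 7.0).
- Drug washout: 0 or 30 days (Section 7.0). The text does not say whether it overlaps the run-in.
- Day 1 to the oral dose on Day 8: 7 days (Section 7.0).
- Last day of a period: Day 10 for Aim 1 only; Day 21 for Aim 2, because Section 5.0 puts the washout after the outpatient follow-up. Discharge on Day 15 is tried as an alternative.
- Washout between periods: 7 to 21 days (Section 5.0).

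**Period 1 oral dose**
- No drug washout: 14 + 7 = 21 days (3.0 weeks).
- Drug washout overlapping the run-in: 30 + 7 = 37 days (5.3 weeks).
- Drug washout followed by the run-in: 30 + 14 + 7 = 51 days (7.3 weeks).

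**Step from the Period 1 to the Period 2 oral dose:** (last day − 8) + washout + 7
- Aim 1 only: 2 + 7 + 7 = 16 to 2 + 21 + 7 = 30 days.
- Aim 2, washout from Day 21: 13 + 7 + 7 = 27 to 13 + 21 + 7 = 41 days.
- Aim 2, washout from Day 15: 7 + 7 + 7 = 21 to 7 + 21 + 7 = 35 days.

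**Period 2 oral dose, days after screening**

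| | Shortest | Longest, no drug washout | Longest, overlapping | Longest, sequential |
|---|---|---|---|---|
| Aim 1 only | 21 + 16 = 37 | 21 + 30 = 51 | 37 + 30 = 67 | 51 + 30 = 81 |
| Aim 2 from Day 21 | 21 + 27 = 48 | 21 + 41 = 62 | 37 + 41 = 78 | 51 + 41 = 92 |
| Aim 2 from Day 15 | 21 + 21 = 42 | 21 + 35 = 56 | 37 + 35 = 72 | 51 + 35 = 86 |

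Each IV dose falls about one day after the oral dose.

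**Activity after the test.** 10 µCi × 2 doses × 2 periods = 40 µCi, which matches Section 10.0. All of it follows the screening test. Half, 20 µCi, is given in Period 2, at least 37 days after the test.

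**Is there a second screening?** Section 10.0 puts 7 mL for screening, 7 mL for baseline and about 160 mL for the absorption test into each period: 7 + 7 + 160 = 174 mL, and 2 × 174 = 348 mL, the stated Aim 1 total. That total therefore counts a screening draw in both periods. No second screening visit is described in Section 5.0 or 7.0. If one took place before Period 2, the 7 diet days would still separate it from dosing, and the Period 1 interval would not change.

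**The case against.** The strongest objection is that the absence is inferred from incomplete material. Section 8.0 leaves the visit schedule to Appendix B. That appendix, the RDRC correspondence (Appendix D) and the consents are not visible, and any of them could require a repeat test or address contraception. The body text is also not a full list of assays: the Day 1 list is introduced as what will be included, and the Day 8 text names no assays for the pre-dose sample. This stands. A reader might infer that pregnancy status is never checked at dosing, but the documents do not support that. They show only that no procedure in the supplied text does so.

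Second, the size can be overdrawn. The 92 days require Aim 2, a drug washout run in sequence with the run-in, and the longest crossover washout. Without a drug washout the longest interval is 62 days. This also stands, although neither figure is a ceiling, because the supplied text sets no maximum time from screening to Day 1.

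Third, few women are concerned and the dose is modest. Section 12.0 plans 50% female among four participants, so two women. Those who are postmenopausal or sterile need no test, so the number affected could be zero. Section 10.0 gives a total effective dose of 35.6 mrem against a US average of 620 mrem per year (35.6 / 620 = 5.7%). These facts limit how often and how much. They do not answer the point: the figure is the subject's own dose, no fetal assessment is given, and the protocol itself chose to exclude pregnancy.

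A reader might also argue that an undetected pregnancy would distort the absorption outcomes. The documents say nothing on this, so the point does not rest on it.

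**Conclusion.** The concern holds for the protocol text as supplied. The pregnancy criterion has no time point relative to P-33 dosing, and the one test placed at a visit precedes the first dose by at least 21 days (37 to 51 with a drug washout) and the Period 2 oral dose by at least 37. The structural minimum carries the point. It assumes that the run-in begins on the day of screening, and any delay lengthens the interval.

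Confidence is moderate because the calendar, the RDRC documents and the consents cannot be checked. The number of women exposed to the gap is small and not stated. Even so, this is more than missing detail: followed as written, the text does not verify the protocol's own exclusion at the point of exposure, and reconciling it costs very little.

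**What to change.** Reconcile Sections 4.1, 4.2 and 7.0 so that the existing requirement to be confirmed not pregnant is tied to the P-33 dosing days in each period, for subjects of childbearing potential. The fasting urine that Section 7.0 already collects on Day 8 before the P-33 beverage can be used for this. The screening test remains the check for entry. This applies the protocol's own criterion to its own schedule; it changes no dose or diet and proposes no new clinical rule.

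First check Appendix B, the RDRC documents and the consents, and align them with the text. If Appendix B already schedules a repeat test, only the body text needs aligning. State also whether the second screening blood draw counted in Section 10.0 corresponds to a visit.

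The cost is one amendment and at most two urine tests per woman of childbearing potential, with no extra visit or blood draw. The small downside is that the result must be available before dosing. The statistical analysis does not change.
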